12. EFFICACY ASSESSMENTS

Determination of efficacy requires two primary assessments.

The first assessment is the clinical read of the ^{68}Ga -PSMA-HBED-CC PET/CT scan. Trained readers will identify lesions positive for prostate cancer disease, and based on these results, will categorize specifically defined anatomical regions of the subject (Table 12.2) as positive for disease by ^{68}Ga -PSMA-HBED-CC PET/CT. Criteria are described in Section 12.1 below.

The second assessment is the reference standard determination of disease positivity or negativity also performed on the same specifically defined anatomical regions (Table 12.2). The reference standard definitions are described below, and consist of a combination of pathological confirmation, conventional imaging follow-up evidence, and serial PSA measurements. Criteria are described in Section 12.2 below.

For purposes of endpoints, four major regions are identified for final analysis as defined in Table 12.1. Each region is divided into subregions as defined in Table 12.2. All primary data from ^{68}Ga -PSMA-HBED-CC PET interpretations, pathology results, and conventional imaging results, will be collected per the subregions defined below. The final region assignments and results will be derived from the subregion data as applicable.

Region	Description
1	Prostate Bed
2	Pelvis outside of prostate bed including lymph nodes
3	Extrapelvic soft tissue, lymph nodes and organ metastases (non-bone)
4	Bone metastases

Table 12-1. Major Analysis Regions

Region 2: Pelvis outside of prostate bed	Region 3: Extrapelvic soft tissue	Region 4: Bone metastases
Right obturator	Lung	Spine
Left obturator	Liver	Ribs
Right external iliac	Pancreas	Pelvis
Left external iliac	Spleen	Extremities
Right internal iliac	Intestine	Skull
Left internal iliac	Mesentary	Sternum
Other pelvic regions	Brain	Clavicle
	Other soft tissue	Other bone
	Abdominal nodes	
	Thoracic nodes	
	Other nodes	

Table 12-2. Subregion Classification

12.1. **^{68}Ga -PSMA-HBED-CC PET Results Definition**

Imaging interpretation ^{68}Ga -PSMA-HBED-CC PET:

Local Interpretations: PET images will initially be interpreted by a board certified nuclear medicine physician or a board-certified radiologist experienced in reading PET at the time of the imaging study at the institution that the study is being performed. These interpretations will not be used for evaluation of the primary endpoint.

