12.1.1.3. Bone lesions will be considered positive if the ^{68}Ga -PSMA-

HBED-CC uptake is focal and greater than physiologic bone marrow.

- Bone lesions will be classified by further by region: spine, ribs, pelvis, extremities, skull, sternum, and clavicle, as Defined in Table 12.2. These sub-regions will be correlated with reference standard results in these sub-regions, however this sub-region data will not be directly used for evaluation of the primary or secondary endpoints, but for exploratory analysis.

12.1.1.4. Prostate bed and prostate lesions will be considered positive if the ⁶⁸Ga-PSMA-HBED-CC uptake is focal and greater than physiologic background activity of the involvement organ or anatomic site.

12.2. Reference standard definition:

12.2.1. Histopathology/Biopsy will be the primary determinate of tissue positivity and negativity for prostate cancer disease. Pathology date, organ, and location as well as any notes related to the pathology will be obtained from the subject chart. The anatomical region/sub-region the pathology occurred in will be assigned by the investigator team:

⁶⁸Ga-PSMA-HBED-CC positive findings are aimed to be confirmed by histopathology/biopsy if clinically feasible. Pathology performed 60 days before or after the ⁶⁸Ga-PSMA-HBED-CC PET will be available for correlation.

Histopathological procedures and biopsies will be performed as clinically indicated and as per institutional protocol.

12.2.1.1. Lymph Nodes, Visceral Lesions, and Bone Lesions positive for disease by pathology.

- Lesions with positive pathologic confirmation will be regarded as positive for disease. The regionality of the resected tissue will be assigned into respective regions and sub-regions as described above in Table 12.2.

12.2.1.2. Lymph Nodes and Visceral Lesions negative for disease by pathology.

- Tissue removed and negative for pathology are considered negative for prostate cancer disease, unless subsequent conventional imaging or ⁶⁸Ga-PSMA-HBED-CC PET imaging demonstrates that targeted tissue were not resected. In this case:

- i. Subjects can be rescanned with dedicated CT, MRI, or ⁶⁸Ga-PSMA-HBED-CC PET/CT to determine if the suspicious ⁶⁸Ga-PSMA-HBED-CC tissue was removed. If the tissue is confirmed as removed, this is considered negative for disease.

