12.2.2.3. Bone lesions will be considered:

i. Positive for disease on baseline assessment:

- Any positive sclerotic lesion on the CT portion of the ⁶⁸Ga-PSMA-HBED-CC PET or on a separate CT obtained \leq 30 days before or after the PET/CT.
- Focal uptake on the baseline bone scan performed within one month of ⁶⁸Ga-PSMA-HBED-CC PET.
- Any MRI lesion in bone read as positive on the initial MRI performed within one month of ⁶⁸Ga-PSMA-HBED-CC PET.

ii. Positive for disease on follow up:

- Any new positive sclerotic lesion on CT within 12 months of ⁶⁸Ga-PSMA-HBED-CC PET scan
- Any new MRI bone lesion within 12 months of ⁶⁸Ga-PSMA-HBED-CC PET scan
- Any new focal uptake in bone within 12 months of ⁶⁸Ga-PSMA-HBED-CC PET scan

- In subjects with localized suspected bone lesion(s) receiving targeted treatment without concomitant systemic treatment:
- If the subject demonstrates a decrease of PSA by greater than 50% after targeted treatment.

iii. Negative for disease:

- Conventional Imaging follow up will not be used for assessment of negativity for disease

iv. Indeterminate for disease:

- Regions with no bone lesions determined to be positive by the conventional imaging criteria described above and without pathology will be designated bone regions indeterminate for prostate cancer disease.

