13.3. Definitions of ^{68}Ga PSMA-HBED-CC accuracy

13.3.1. True positive definitions

13.3.1.1. **^{68}Ga PSMA-HBED-CC PET/CT positive for nodal metastases by internal blind reader** – and pathology (if available) positive for that node, or node positive for disease by imaging as defined in Section 12.2.2.1 If this criteria is met, the subject is defined as true positive for nodal disease.

13.3.1.2. **^{68}Ga PSMA-HBED-CC PET/CT positive for visceral metastases by internal blind reader** – and pathology (if available) positive for that visceral lesion, or, visceral lesion positive for disease by imaging as defined in Section 12.2.2.2. If this criteria is met, the subject is defined as true positive for visceral disease.

13.3.1.3. **^{68}Ga PSMA-HBED-CC PET/CT positive for osseous**

metastases by internal blind reader - and pathology (if available) positive for that osseous lesion, or, osseous lesion positive for disease by imaging as defined in Section 12.2.2.3. If this criteria is met, the subject is defined as true positive for osseous disease.

13.3.1.4. A single nodal, visceral, or osseous region determined as true positive as defined above is sufficient to define the subject as true positive by ⁶⁸Ga PSMA-HBED-CC PET/CT.

13.3.2. **True negative definitions**

13.3.2.1. **⁶⁸Ga PSMA-HBED-CC PET/CT negative for nodal metastases by internal blind reader** – and pathology (if available) negative for disease, and, extra-pelvic node not positive for disease by imaging. If this criteria is met, the subject is defined as true negative for nodal disease.

13.3.2.2. **⁶⁸Ga PSMA-HBED-CC PET/CT negative for visceral metastases by internal blind reader** – and pathology (if available) negative for disease, and, visceral lesion not positive for disease by imaging. If this criteria is met, the subject is defined as true negative for visceral disease.

13.3.2.3. **⁶⁸Ga PSMA-HBED-CC PET/CT negative for osseous metastases by internal blind reader** - and pathology (if available) negative for disease, and, osseous lesion not positive for disease by imaging. If this criteria is met, the subject is defined as true negative for osseous disease.

13.3.3. **False positive definitions:**

13.3.3.1. **⁶⁸Ga PSMA-HBED-CC PET/CT positive for nodal metastases by internal blind reader**, pathology (if available) is negative, and imaging demonstrates that node is not positive for disease. If this criteria is met, the subject is defined as false positive for nodal disease.

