- 13.3.4.3. **^{68}Ga PSMA-HBED-CC PET/CT negative for osseous lesion by internal blind reader**, and pathology (if available) positive for any osseous lesion, or, osseous lesion positive for disease by imaging as defined in Section 12.2.2.3. If this criteria is met, the subject is defined as false negative for osseous disease.
- 13.3.4.4. A subject is defined as false negative for disease by ^{68}Ga PSMA-HBED-CC PET/CT if the subject is negative for disease in all regions by ^{68}Ga PSMA-HBED-CC PET/CT, but positive for disease by pathology or follow-up imaging in any region.

13.3.5. **Non-evaluable definitions:**

- 13.3.5.1. Any region that does not have sufficient data to meet the criteria for definition of true positive region, true negative region, false positive region, or false negative region will be classified as non-evaluable.
- 13.3.5.2. Any region that does not have sufficient data to meet the

criteria for definition of true positive subject, true negative subject, false positive subject, or false negative subject will be classified as non-evaluable.

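### Imaging can confirm a PET-positive bone finding through a lesion elsewhere in the skeleton, because section 12.2.2.3 asks for no match of site

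*Combined protocol and SAP*

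**What the plan says.** All references are to the combined protocol and SAP.

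- **Reference standard for bone, follow-up (12.2.2.3(ii)).** Bone is positive on "Any new positive sclerotic lesion on CT within 12 months of" the PET scan, "Any new MRI bone lesion within 12 months of" it, or "Any new focal uptake in bone within 12 months of" it. A further route, for localized bone lesions given targeted treatment alone, rests on a PSA fall.
- **Reference standard for bone, baseline (12.2.2.3(i)).** Any sclerotic CT lesion, focal bone-scan uptake or positive MRI bone lesion around the time of PET suffices. No site is specified here either.
- **Unit of analysis (section 12, Table 12-1).** "For purposes of endpoints, four major regions are identified for final analysis", and the whole skeleton is Region 4. Spine, ribs, pelvis, extremities and so on are sub-regions in Table 12-2, but 12.1.1.3 says "this sub-region data will not be directly used for evaluation of the primary or secondary endpoints".
- **True positive, bone (13.3.1.3).** PET-positive bone is confirmed by pathology "positive for that osseous lesion, or, osseous lesion positive for disease by imaging as defined in Section 12.2.2.3".
- **Subject level (13.3.1.4).** "A single nodal, visceral, or osseous region determined as true positive as defined above is sufficient to define the subject as true positive".
- **Location check (13.3.3.6).** Positive pathology in a different bone region from the PET finding is a false positive. Imaging has no counterpart.
- **False negative, bone (13.3.4.3).** PET-negative bone with pathology "positive for any osseous lesion, or, osseous lesion positive for disease by imaging as defined in Section 12.2.2.3" is false negative for bone. Under 13.3.4.4 the subject is false negative only if PET is negative in every region. Section 5.6 restricts false negatives to biopsy-proven lesions that PET missed and conventional imaging showed.

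**The concern.** The objectives in 1.1.1 and 1.2.1 concern detection of tumor location. A reference standard for that question has to ask whether disease is present where PET placed it. For bone, the imaging route asks only whether a qualifying lesion exists somewhere in the skeleton, at baseline or newly within a year.

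Take a man with false rib uptake at baseline and a new lesion in an extremity at month 11. Read literally, 12.2.2.3(ii) makes Region 4 positive, 13.3.1.3 makes his bone finding true positive, and 13.3.1.4 makes him a true-positive subject. He then enters the primary sensitivity and the per-subject and per-region PPV as a success, although the scan located nothing correctly.

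The opposite error is possible but rarer. A man negative on PET in every region, who has imaging during the year, can become a false negative through a bone lesion that may have formed after the scan.

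In both cases the classification depends on what happens during follow-up, and not only on the scan. The estimate is meant to inform the power of a larger study (13.1).

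**Working it through.** **1. Is a site match supplied anywhere for bone imaging?**

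| Place | Ties confirmation to the PET site? |
|---|---|
| 12.2.2.3(i), (ii) | No |
| Table 12-1, Region 4 | No; all bone is one region |
| 12.1.1.3 | No; sub-regions are kept out of the endpoints |
| 13.3.1.3, pathology branch | Yes, to the same lesion |
| 13.3.1.3, imaging branch | No; it points back to 12.2.2.3 |
| 13.3.3.6 | Yes, for pathology only |
| 5.6.2, 6.4.3, 12.2.2 | They direct follow-up at PET-positive lesions, but are not classification rules |

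**2. The plan's own figure.** Section 13.1 gives half-widths for N = 30 by the normal approximation, 1.96 × √(p(1 − p)/30). At p = 0.80 this is 1.96 × √(0.16/30) = 14.3 points, as printed. The other four also reproduce: 16.4, 15.5, 12.8 and 10.7. The point disputes none of them.

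**3. Formulas used.** Sensitivity = TP/(TP + FN); PPV = TP/(TP + FP). Section 13.1 prints sensitivity with FP in the denominator. That is a separate error, and the usual definition is used here.

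**4. Confirmation by an unrelated lesion.** The documents give no rate of new bone lesions, so all counts are assumed: 20 TP with 5 FN for sensitivity, and 20 TP with 4 FP for PPV. These are separate illustrations. Combined with the two added men they would total 31, one above the planned 30, so they are not a projected cohort.

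Without the unrelated lesion, what would the two men have been? Section 12.2.2.3(iii) and (iv) bar imaging from showing bone to be negative and leave unconfirmed bone without pathology indeterminate. If nothing else classifies the men, 13.3.5 makes them non-evaluable. Moving two from non-evaluable to true positive gives:

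- Sensitivity: 20/25 = 80.0% to 22/27 = 81.5% (+1.5 points).
- Per-subject PPV: 20/24 = 83.3% to 22/26 = 84.6% (+1.3 points).

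If both would instead have been false positive, PPV goes from 20/24 = 83.3% to 22/24 = 91.7% (+8.3 points). The sensitivity change is the same.

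**5. Late lesion counted as a miss.** If two men negative on PET in all regions become false negative, sensitivity goes from 20/25 = 80.0% to 20/27 = 74.1% (−5.9 points).

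**6. Range under another assumed split.** Take 24 TP and 6 FN, 24/30 = 80.0% (Wilson 95% interval 62.7 to 90.5), and let k subjects be classified only through such a lesion.

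| k | k true positives become non-evaluable | k false negatives removed |
|---|---|---|
| 1 | 23/29 = 79.3% | 24/29 = 82.8% |
| 2 | 22/28 = 78.6% | 24/28 = 85.7% |
| 3 | 21/27 = 77.8% | 24/27 = 88.9% |
| 4 | 20/26 = 76.9% (57.9 to 89.0) | 24/26 = 92.3% (75.9 to 97.9) |

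Each such true positive is worth a little under 1 point, and each such false negative about 3. The two act in opposite directions.

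**The case against.** The strongest reply is that the plan means the same lesion. Section 5.6.2 says PET-positive bone lesions are the ones followed, 6.4.3 tells follow-up readers where they are, and 12.2.2 says conventional imaging mainly targets them. On that view, confirming a rib by a lesion in an extremity is an unkind reading of loose wording. This stands as evidence of intent, and a reader should not infer that the authors wanted distant lesions to count. But none of these sections says how a lesion elsewhere is classified, and the location check that was written covers pathology alone.

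Bone is not unique. Sections 13.3.1.1 and 13.3.1.2 also attach the word 'that' only to pathology, and 12.2.2.2(i)(b) accepts a PSA fall without a lesion measurement. The node and visceral imaging rules do, however, mostly rest on size change in lesions already seen. Bone accepts a new one.

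Two stronger readings are tempting and fail.

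- **Any man with PET-negative bone and a later bone metastasis counts against the primary endpoint.** He does not. Sensitivity is per subject, and 13.3.4.4 requires PET to be negative in every region. Section 12.2.2 limits follow-up imaging to PET-positive subjects (6.4.3 does not repeat the limit), so such a man enters mainly through standard-of-care imaging. Section 5.6 would exclude him without a biopsy.
- **PPV is typically inflated to 91.7%.** That needs the men to be false positive otherwise, whereas unbiopsied, unconfirmed bone is normally indeterminate. Section 13.3.3.5 can be read as allowing imaging to establish a false positive, but this conflicts with 12.2.2.3(iii).

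Finally, this is a pilot without significance testing, and 13.1 admits uncertainty about the reference standard. That limits the consequence but does not settle how such a subject is scored.

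**Conclusion.** The point holds in this form: as written, imaging of a lesion anywhere in the skeleton, at baseline or new within 12 months, can turn a PET-positive bone finding and its subject into a true positive. The definition therefore does not measure detection of tumor location for bone.

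The usual size is modest: about +1.5 points on sensitivity and +1.3 on per-subject PPV for two affected subjects. The +8.3 points on PPV applies only where they would otherwise have been false positive. Subjects already true positive through another region are unaffected at subject level.

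The false-negative effect is real under 13.3.4.4 but reaches few subjects. It also depends on an unresolved conflict with 5.6. Because the two effects oppose each other, a reader who infers that the primary sensitivity is biased upward, or downward, goes beyond the documents.

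All counts are assumptions. The absence of a matching rule and the conflict between 5.6 and 13.3.4 do not depend on them. The change should be made before the images are classified.

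**What to change.** 1. In 12.2.2.3(i) and (ii), and in the imaging branch of 13.3.1.3, let an imaging lesion confirm PET-positive bone only if it lies in the same Table 12-2 bone sub-region as the PET uptake, and is the same lesion where that can be identified. Changing (ii) alone would leave the baseline route open.
2. Amend 12.1.1.3 so that bone sub-region data may be used for this match.
3. State that a lesion elsewhere leaves the PET-positive bone indeterminate unless it is confirmed in another way.
4. Reconcile 5.6 with 13.3.4 on what establishes a false negative.
5. Flag false negatives that rest only on a bone lesion first seen on follow-up, and report the primary sensitivity with and without them.

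The cost is mainly wording, since section 12 already has PET, pathology and imaging data collected by sub-region. A few bone regions will become indeterminate. The definition may also differ from that of other sites whose results might be combined under 13.1, so results under the plan's present rule can be reported alongside.

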Secondary: PPVs on a per-subject and per-region-basis of ^{68}Ga PSMA-HBED-CC for detection of tumor location confirmed by histopathology/biopsy and conventional imaging follow-up will be calculated and reported along with the corresponding two-sided 95% confidence intervals. The confidence intervals will be constructed using the Wilson score method.

The following definitions will define accuracy of ^{68}Ga PSMA-HBED-CC for detection of tumor location confirmed by histopathology/biopsy and conventional imaging follow-up

No statistical significance will be generated due to the pilot nature of the project.

13.3. Definitions of ^{68}Ga PSMA-HBED-CC accuracy

13.3.1. True positive definitions

13.3.1.1. **^{68}Ga PSMA-HBED-CC PET/CT positive for nodal metastases by internal blind reader** – and pathology (if available) positive for that node, or node positive for disease by imaging as defined in Section 12.2.2.1 If this criteria is met, the subject is defined as true positive for nodal disease.

13.3.1.2. **^{68}Ga PSMA-HBED-CC PET/CT positive for visceral metastases by internal blind reader** – and pathology (if available) positive for that visceral lesion, or, visceral lesion positive for disease by imaging as defined in Section 12.2.2.2. If this criteria is met, the subject is defined as true positive for visceral disease.

13.3.1.3. **^{68}Ga PSMA-HBED-CC PET/CT positive for osseous**

metastases by internal blind reader - and pathology (if available) positive for that osseous lesion, or, osseous lesion positive for disease by imaging as defined in Section 12.2.2.3. If this criteria is met, the subject is defined as true positive for osseous disease.

13.3.1.4. A single nodal, visceral, or osseous region determined as true positive as defined above is sufficient to define the subject as true positive by ⁶⁸Ga PSMA-HBED-CC PET/CT.

13.3.2. **True negative definitions**

13.3.2.1. **⁶⁸Ga PSMA-HBED-CC PET/CT negative for nodal metastases by internal blind reader** – and pathology (if available) negative for disease, and, extra-pelvic node not positive for disease by imaging. If this criteria is met, the subject is defined as true negative for nodal disease.

13.3.2.2. **⁶⁸Ga PSMA-HBED-CC PET/CT negative for visceral metastases by internal blind reader** – and pathology (if available) negative for disease, and, visceral lesion not positive for disease by imaging. If this criteria is met, the subject is defined as true negative for visceral disease.

13.3.2.3. **⁶⁸Ga PSMA-HBED-CC PET/CT negative for osseous metastases by internal blind reader** - and pathology (if available) negative for disease, and, osseous lesion not positive for disease by imaging. If this criteria is met, the subject is defined as true negative for osseous disease.

13.3.3. **False positive definitions:**

13.3.3.1. **⁶⁸Ga PSMA-HBED-CC PET/CT positive for nodal metastases by internal blind reader**, pathology (if available) is negative, and imaging demonstrates that node is not positive for disease. If this criteria is met, the subject is defined as false positive for nodal disease.

13.3.3.2. **⁶⁸Ga PSMA-HBED-CC PET/CT positive for nodal metastases by internal blind reader**, but pathology (if available) is positive for node but in a different nodal region than the node seen on PSMA PET. If this criteria is met, the subject is defined as false positive for nodal disease.

13.3.3.3. **⁶⁸Ga PSMA-HBED-CC PET/CT positive for visceral lesion by internal blind reader**, pathology (if available) is negative, and imaging demonstrates that the visceral lesion is not positive for disease. If this criteria is met, the subject is defined as false positive for visceral disease.

13.3.3.4. **⁶⁸Ga PSMA-HBED-CC PET/CT positive for visceral lesion by internal blind reader**, but pathology (if available) is positive for visceral lesion but in a different region than the visceral

region seen on PSMA PET. If this criteria is met, the subject is defined as false positive for visceral disease.

- 13.3.3.5. **^{68}Ga PSMA-HBED-CC PET/CT positive for osseous lesion by internal blind reader**, pathology (if available) is negative, and imaging demonstrates that the osseous lesion is not positive for disease. If this criteria is met, the subject is defined as false positive for osseous disease.
- 13.3.3.6. **^{68}Ga PSMA-HBED-CC PET/CT positive for osseous lesion by internal blind reader**, but pathology (if available) is positive for osseous lesion but in a different region than the osseous region seen on PSMA PET. If this criteria is met, the subject is defined as false positive for osseous disease.
- 13.3.3.7. A subject is defined as false positive for disease by ^{68}Ga PSMA-HBED-CC PET/CT if one or more regions as defined above are defined as false positive regions and the subject is not defined as true positive as defined in Section 13.3.1

13.3.4. **False negative definitions:**

- 13.3.4.1. **^{68}Ga PSMA-HBED-CC PET/CT negative for nodal metastases by internal blind reader**, and pathology (if available) positive for any node or positive for disease by imaging as defined in Section 12.2.2.1. If this criteria is met, the subject is defined as false negative for nodal disease.
- 13.3.4.2. **^{68}Ga PSMA-HBED-CC PET/CT negative for visceral lesion by internal blind reader**, and pathology (if available) positive for any visceral lesion, or, visceral lesion positive for disease by imaging as defined in Section 12.2.2.2. If this criteria is met, the subject is defined as false negative for visceral disease
- 13.3.4.3. **^{68}Ga PSMA-HBED-CC PET/CT negative for osseous lesion by internal blind reader**, and pathology (if available) positive for any osseous lesion, or, osseous lesion positive for disease by imaging as defined in Section 12.2.2.3. If this criteria is met, the subject is defined as false negative for osseous disease.
- 13.3.4.4. A subject is defined as false negative for disease by ^{68}Ga PSMA-HBED-CC PET/CT if the subject is negative for disease in all regions by ^{68}Ga PSMA-HBED-CC PET/CT, but positive for disease by pathology or follow-up imaging in any region.

13.3.5. **Non-evaluable definitions:**

- 13.3.5.1. Any region that does not have sufficient data to meet the criteria for definition of true positive region, true negative region, false positive region, or false negative region will be classified as non-evaluable.
- 13.3.5.2. Any region that does not have sufficient data to meet the

criteria for definition of true positive subject, true negative subject, false positive subject, or false negative subject will be classified as non-evaluable.

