ii. If ^{68}Ga -PSMA-HBED-CC PET/CT positive tissue is still present, a needle biopsy can be pursued at the discretion of the treating physician. Images of the procedure will be reviewed to determine if the correct tissue was biopsied.

- If the ^{68}Ga -PSMA-HBED-CC PET/CT positive tissue was biopsied, a negative pathologic finding of the biopsied tissue is considered negative for disease.
- If the ^{68}Ga -PSMA-HBED-CC PET/CT positive tissue was biopsied, a positive pathologic finding of the biopsied tissue is considered positive for disease.
- If biopsy or re-biopsy is not performed, or the wrong tissue was biopsied, change in node size as measured by conventional imaging and as defined below will be the criteria by which disease status will be defined.

12.2.1.3. Bone lesions: Given the high rate of false negative biopsies for osseous metastases in subjects with prostate cancer, subjects with negative bone biopsies of ^{68}Ga -PSMA-HBED-CC PET positive lesions will be further evaluated:

- If pathology demonstrates an alternative diagnoses that is known to be ^{68}Ga -PSMA-HBED-CC positive (eg Renal Cell Carcinoma metastases, Paget's disease), then this will be considered negative for disease.
- If pathology is indeterminate, then follow-up imaging as described below will be performed as per clinical standards at the site.

12.2.1.4. Although not routinely performed during standard practice, immunohistochemical staining for PSMA of tumor specimens (primary and lymph node metastases) may be performed, although not required.

12.2.1.5. All regions not sampled for biopsy/histopathology will be designated as indeterminate for disease by pathology. Conventional imaging follow-up may be used in these cases to determine tissue status.

12.2.2. Follow-up Imaging will be used as a secondary assessment for prostate cancer in the event pathology information is not available:

All subjects will be tracked for follow-up conventional imaging between 3-12 months post ^{68}Ga -PSMA-HBED-CC (dedicated CT, MRI and/or bone scan) as per site standard of care. If no follow-up imaging has been performed within the 9 months following the ^{68}Ga -PSMA-HBED-CC scan, then the research study will pay for an additional follow-up CT scan to be performed

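### For a PET-positive lesion with a sound negative biopsy and positive follow-up imaging, section 12.2 gives a false positive, but 13.3 gives a true positive or non-evaluable

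*Combined protocol and SAP*

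**What the plan says.** Section 12.2.1 sets the reference standard: "Histopathology/Biopsy will be the primary determinate of tissue positivity and negativity for prostate cancer disease". Section 12.2.2 then gives imaging its place: "Follow-up Imaging will be used as a secondary assessment for prostate cancer in the event pathology information is not available". For nodes and visceral lesions, 12.2.1.2 says "Tissue removed and negative for pathology are considered negative for prostate cancer disease", with an exception when later imaging shows that the target was not resected. If the PET-positive tissue itself was then biopsied and was negative, the lesion is negative. If the wrong tissue was sampled, or no biopsy or re-biopsy was done, change in node size decides. For bone, 12.2.1.3 treats an alternative diagnosis known to take up the tracer as negative and sends indeterminate pathology to follow-up imaging.

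Section 13.3 turns this into counts. A PET-positive lesion is a true positive as follows:

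- nodes (13.3.1.1): "and pathology (if available) positive for that node, or node positive for disease by imaging as defined in Section 12.2.2.1"
- visceral lesions (13.3.1.2): "and pathology (if available) positive for that visceral lesion, or, visceral lesion positive for disease by imaging as defined in Section 12.2.2.2"
- bone (13.3.1.3): "and pathology (if available) positive for that osseous lesion, or, osseous lesion positive for disease by imaging as defined in Section 12.2.2.3"

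A node is a false positive (13.3.3.1) when "pathology (if available) is negative, and imaging demonstrates that node is not positive for disease". Sections 13.3.3.3 and 13.3.3.5 use the same form for visceral lesions and bone. At subject level, 13.3.3.7 makes a subject false positive only if a region is false positive "and the subject is not defined as true positive as defined in Section 13.3.1". Whatever fits no rule is non-evaluable (13.3.5).

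**The concern.** The two sections classify one kind of lesion differently, and an analyst cannot follow both. PPV, per subject and per region, is the secondary endpoint (13.2), and these are exactly the lesions that should count against it.

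The imaging criterion that competes with the biopsy can be met by response to treatment. Under 12.2.2.1, a suspicious node in a man on systemic therapy is positive if its short axis falls by more than 30% and PSA falls by more than 50%. Unlike the size rules for targeted treatment and for untreated men, this one has no 3 mm minimum.

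The false-negative rules (13.3.4.1 to 13.3.4.3) also join pathology and imaging by an either/or. A PET-negative site with negative pathology and positive imaging would be a false negative under 13.3 but not under 12.2.

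Section 13.1 says the results will set the target sensitivity for a larger study and may be combined with sites using the same reference standard definitions. That needs one definition, fixed before anyone sees how the lesions score.

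**Working it through.** **The plan's own figures.** The only numerical planning figures are the half-widths in 13.1 for n = 30. With 1.96 × √(p(1−p)/30), p = 0.80 gives 1.96 × √(0.16/30) = 14.3%. The other four also reproduce: 16.4, 15.5, 12.8 and 10.7%. No PPV or pathology/imaging discordance rate is stated.

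**The rules side by side, for a PET-positive lesion**

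| Pathology | Imaging criterion of 12.2.2 | Under 12.2 | Under 13.3 |
|---|---|---|---|
| Node or visceral, right tissue, negative | not met | negative: false positive | false positive |
| Node or visceral, right tissue, negative | met | negative: false positive | true positive; non-evaluable if the either/or is read as a hierarchy |
| Bone, alternative tracer-avid diagnosis | met (e.g. sclerotic on baseline CT, 12.2.2.3) | negative: false positive | same as the row above |
| Node, wrong tissue sampled | met | imaging decides: true positive | true positive |
| Bone, indeterminate | met | imaging decides: true positive | true positive |
| None | not met | indeterminate | false positive |

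Rows 2 and 3 are the point. On the hierarchy reading, imaging no longer makes the lesion a true positive. It still fails the false-positive rule, because imaging is positive, and so drops to non-evaluable under 13.3.5.1. On neither reading is it the false positive that 12.2 requires. Row 6 is a second mismatch and works in the opposite direction.

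**Size for rows 2 and 3.** PPV = TP/(TP+FP), with Wilson 95% intervals as in 13.2. Two inputs are assumptions: 30 evaluable PET-positive subjects (the full planned sample), and d = 0 to 3 subjects whose only scored lesion is of this kind. A subject with another true-positive region is unchanged at subject level. Start from 24 TP and 6 FP under 12.2:

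| d | 12.2 | 13.3, literal: (24+d)/30 | 13.3, non-evaluable: 24/(30−d) |
|---|---|---|---|
| 0 | 80.0% (62.7–90.5) | 80.0% | 80.0% |
| 1 | 80.0% | 83.3% (66.4–92.7) | 82.8% (65.5–92.4) |
| 2 | 80.0% | 86.7% (70.3–94.7) | 85.7% (68.5–94.3) |
| 3 | 80.0% | 90.0% (74.4–96.5) | 88.9% (71.9–96.1) |

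Per subject, the literal reading adds 1/30 = 3.3 points. On the non-evaluable reading, the first subject adds TP/29 − TP/30 = TP/870. That is 21/870 = 2.4, 24/870 = 2.8 and 27/870 = 3.1 points from base PPVs of 70, 80 and 90%.

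**Adding row 6.** Assume 24 TP and 3 biopsy-proven FP under 12.2, so PPV = 24/27 = 88.9%. With d = 2, the literal rule gives 26/27 = 96.3%. Adding 2 imaging-only false positives gives 26/29 = 89.7%, and adding 3 gives 26/30 = 86.7%. The net shift can be up or down.

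**Sensitivity.** Taken as TP/(TP+FN), with 24 TP and an assumed 3 FN, it is 24/27 = 88.9%. At d = 3 it is 27/30 = 90.0%, a change of 1.1 points. Section 13.1 prints FP where FN belongs in the denominator. Computed that way, sensitivity would take the full PPV shift, but that is a separate error.

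**The case against.** The best defence is that the hierarchy carries over. Section 13.3.1 imports imaging by reference to subsections of 12.2.2, which applies when pathology is unavailable, and with the qualifier about availability the either/or can be read as otherwise. This stands as a possible reading. It changes the outcome from true positive to non-evaluable but does not restore the false positive.

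A reader might infer that 13.3 lets imaging overrule any negative biopsy. The documents do not support that. Section 12.2 itself hands the decision to imaging after mis-targeted sampling or indeterminate bone pathology, and 12.2.1.3 cites a high false-negative rate for bone biopsies. The clear bone conflict is limited to an alternative tracer-avid diagnosis. It should be rare, since 3.2.3 and 3.2.4 exclude known Paget's disease and other malignancy.

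A reader might also infer that a false positive always needs both sources, or that 13.3 as a whole inflates PPV. Neither holds. Without pathology, imaging alone can give a false positive, and 13.3.3.2, 13.3.3.4 and 13.3.3.6 add a route through positive pathology in a different region.

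Nor do the documents support a PPV driven to 100% because biopsy-negative lesions lack later imaging and become non-evaluable. Under 12.2.2 the study arranges a CT for PET-positive subjects not imaged within 9 months, and under 6.4.3 readers are told the lesion locations. That leaves mainly dropouts and lesions outside the abdomen and pelvis.

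Finally, this is a pilot with no hypothesis test, PPV is secondary, and the number of affected subjects is unknown. That limits the severity but does not remove the contradiction.

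**Conclusion.** The contradiction holds for PET-positive lesions with determinate negative pathology from correctly targeted tissue that also meet an imaging criterion. Section 12.2 makes them false positives and 13.3 never does. For these lesions the shift in PPV is always upward, by about 3 points per subject. This assumes 30 evaluable PET-positive subjects and that the lesion determines the subject's status. With fewer evaluable subjects, each one weighs more.

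The documents give no basis for the number of such subjects, so the total effect cannot be stated. The net bias of 13.3 has no fixed sign, because its imaging-only false positives, which 12.2.2 calls indeterminate, pull PPV down. The effect on TP/(TP+FN) is small beside the planned half-widths of 10.7 to 16.4 points. The false-negative wording should seldom matter: study-arranged imaging is limited to PET-positive subjects (12.2.2), 5.6 takes false negatives only from positive biopsies, and 13.3.4.4 requires a PET scan negative in all regions.

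This should be fixed before scoring, since choosing between the sections after the results are known would be a post hoc choice.

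**What to change.** Reword 13.3.1.1 to 13.3.1.3, 13.3.3.1, 13.3.3.3, 13.3.3.5 and 13.3.4.1 to 13.3.4.3 at lesion level:

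1. Determinate pathology from the correctly targeted lesion decides that lesion, positive or negative. Negative gives a false positive for a PET-positive lesion, with no imaging condition.
2. The imaging criteria of 12.2.2 apply only when pathology of that lesion is absent, mis-targeted (12.2.1.2) or indeterminate (12.2.1.3).
3. A lesion without pathology that meets no imaging criterion is indeterminate, hence non-evaluable, as 12.2.2 states.
4. A region stays positive if any other lesion in it is positive by the reference standard, so that one negative biopsy does not cancel a second lesion.

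Define determinate and correctly targeted by reference to 12.2.1.2 and 12.2.1.3. State also how to score a negative bone biopsy that shows no alternative diagnosis, since 12.2.1.3 promises further evaluation but spells out only the alternative-diagnosis and indeterminate cases. Reporting the number of lesions on which pathology and imaging disagree would show how much the rule matters.

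The cost is wording only, with no new data or procedures. Some regions will move to non-evaluable, and the reported PPV may shift in either direction.
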